h. Perform complete blood count (Hemoglobin, Hematocrit, RBC, WBC, Platelets) with differential (Neutrophils, Lymphocytes, Monocytes, Eosinophils, Basophils) at week 1 and week 2 for the first 4 cycles and thereafter at the expected time of nadir (lowest count of any type of blood cell).

i. Laboratory tests comprise of calcium, magnesium, and potassium before every dose of cetuximab therapy and for at least 8 weeks following the completion of cetuximab. Replete electrolytes as necessary.

j. Send tissue slides to the central laboratory (see lab manual). Collected at baseline, and at the time of surgery [UPTEN, EGFR and EGFR-pathway associated genes (TGF-a, CRYAB, NRAS, KRAS, AKT3, PTEN, MEK1 and KRAS amplicon genes). Additional exploratory biomarkers may include (but are not limited to) beta tubulin isoforms, ABC transporters, TACC3, HCAPG, GTSE1, Kallikreins and defined gene models associated with ixabepilone response. Tumor biomarkers will be assessed on a formalin-fixed, paraffin-embedded (TFFPET) tumor sample from a previous biopsy (baseline) and from the surgical specimen. A minimum of 15 slides will be collected at each time.

k. Serum sample for biomarkers expression at baseline, and at the time of surgery. ** Optional (Serum sample for biomarkers expression will be done at later time).
 I. A 12-lead ECG with QT measurement should be performed at screening, at the end of study/early termination, and whenever medically indicated. An Echocardiogram should be performed at screening only and whenever medically indicated.

m. Evaluate tumor response using RECIST criteria before chemotherapy and before surgery (from randomization to disease progression or until surgery).

n. Subjects who are to receive ixabepilone are to be premedicated approximately 1 hour before the infusion with both an oral H1 blocker (diphenhydramine 50 mg or equivalent) and an oral H2 blocker (eg, ranitidine 150-300 mg or cimetidine 300–800 mg or nizatidine 150-300 mg or famotidine 20–40 mg); premedication with steroids is indicated in subjects who developed a hypersensitivity reaction to ixabepilone in previous cycles. Subjects who are to receive cetuximab are to be premedicated with an H1 antagonist (e.g., 50 mg of diphenhydramine IV)

o. Monitor the subject for hypersensitivity reactions during and after all infusions.

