2.5 Post-neoadjuvant Surgical Intervention

Within 3 - 4 weeks of completing neoadjuvant therapy, patients will undergo surgery of the breast and axilla according to local guidelines. Patients will remain in the study throughout the neoadjuvant therapy, regardless of type, until the completion of surgical intervention and the collection of the post-neoadjuvant therapy biopsy. Portions of tumor tissue from the primary site, or lymph nodes (when available), will be obtained for post treatment biomarkers expression studies.

Note: please collect all tissue slides (15 at baseline and 15 after surgery) at the site before send it out to the central lab (see lab manual)

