3.0 Biomarkers Research Assessment

3.0.1 Biomarkers Exploratory Research Tumor Tissue Collection

Two samples of tumor tissue will be collected during the course of the study. The first sample will be collected prior to treatment with the study drug and the second at the time of the surgery. These samples will be used to obtain mRNA for analysis of tumor gene expression. Tumor biomarkers will be assessed on a formalin-fixed, paraffin-embedded (FFPE) tumor sample from a previous biopsy (baseline) and from the surgical specimen. A minimum of 15 slides will be collected at each time. Details for processing, storing and shipping these samples will be provided by BMS in the CA163157 Procedure Manual.

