3.0.3 Biomarkers Exploratory Research Tumor Tissue Collection

Any patient, who switches to another neoadjuvant therapy prior to surgery, will be asked to undergo an additional breast biopsy. This breast biopsy is optional and will require an additional consent. The biopsy must be obtained within 21 days after last dose of study drug and prior to next therapeutic regimen. Details for processing storing and shipping these samples will be provided by BMS in the CA163157 Procedure Manual.

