8.0 CRITERIA FOR RESPONSE

8.0.1 PATHOLOGICAL RESPONSE: The histologic response after treatment will be evaluated in the primary tumor and in the axillary lymph nodes removed by axillary dissection. In the primary tumor, cellular modifications will be evaluated in both the infiltrating tumoral component and in the possible ductal component, if applicable:

- Analysis of the viable residual infiltrating component (% of total tumoral mass)

- Analysis of the residual ductal component (% of total tumoral mass)
- Determination of the mitotic index.

In the axillary lymph nodes: analysis of the viable residual component. The criteria of pathological response will be defined according to the Sataloff Classification ⁴⁶.

The response in the primary tumor site will be graded from A to D.

Primary site response:

T-A Total or near total therapeutic effect.

T-B Subjectively greater than 50% therapeutic effect but less than total or near total.

T-C Less than 50% therapeutic effect, but effect evident

T-D No therapeutic effect.

Axillary lymph node response:

N-A Evidence of therapeutic effect, no metastatic disease.

N-B No nodal metastasis or therapeutic effect.

N-C Evidence of therapeutic effect but nodal metastasis still

Present.

N-D Viable metastatic disease, no therapeutic effect

pCR corresponds to pathological grades T-A; N-A, N-B.

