12.2 Statistical analysis

All major treatment comparisons between the two randomized groups in this trial will be performed according to the principle of "intention-to-treat", that is, subjects

CA163-157 Clinical Protocol

will be analyzed according to the treatment arm to which patients were randomized, regardless of compliance to assigned treatment. Summary statistics will be provided for overall response rates and pCR rates by treatment arm. The different rates between treatment arms will be compared by Cochran-Mantel-Haenszel test. . Logistic regression models will be used to assess the association between expression of biomarkers (such as PTEN, EGFR and EGFR-pathway associated genes (including, but not limited to TGF- α , CRYAB, NRAS, KRAS, AKT3, PTEN, MEK1 and KRAS amplicon genes) from the baseline and the overall objective or pathologic response, controlled by treatment arm, age, and disease stage. The unpaired t-test will be applied to compare the difference of expression of biomarkers between the baseline and at surgery in the two arms. Benjamini and Hochberg adjustment will be used to adjust multiple comparisons in expressions of all marks. Safety and toxicity of each regimen will be tabulated by type and grade at the end of chemotherapy. Radiographic efficacy assessment will be performed on all patients at the end of chemotherapy. Statistical significance is defined as 2-tailed p=0.05 level. Stata Version 10 (College Station, TX) will be used for all statistical analyses.

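### Section 12.2 gives only an unpaired t-test for the baseline-to-surgery biomarker comparison: the wrong test for a within-arm contrast, and the right one between arms but limited to patients with tumour at surgery

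*Combined protocol and SAP*

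**What the plan says.** Section 12.2 has one sentence on marker change: "The unpaired t-test will be applied to compare the difference of expression of biomarkers between the baseline and at surgery in the two arms". It follows this with a Benjamini-Hochberg adjustment across markers. It names no paired method, no analysis set for this comparison, and no rule for a patient with no tumour left to sample.

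The sampling is paired by design. Section 3.0.1 says of the tumour samples: "The first sample will be collected prior to treatment with the study drug and the second at the time of the surgery". It adds "A minimum of 15 slides will be collected at each time". Section 2.5 describes the surgical material: "Portions of tumor tissue from the primary site, or lymph nodes (when available), will be obtained for post treatment biomarkers expression studies".

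Section 8.0.1 defines the primary outcome: "pCR corresponds to pathological grades T-A; N-A, N-B", where the breast grade is "T-A Total or near total therapeutic effect". Section 12.1 plans 54 patients per arm, with pCR of 18% on ixabepilone and 43% on the combination.

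Biomarker work is listed as exploratory in section 1.3. The stated aim there is correlation with response, which section 12.2 handles separately by logistic regression on baseline markers.

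**The concern.** The sentence supports two different analyses, and an analyst would have to guess between them.

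If baseline values are set against surgical values within an arm, an unpaired test treats two measurements on one patient as independent. With positive correlation the standard error is too large, and real changes are missed.

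If per-patient changes are compared between arms, the unpaired test suits two independent groups. The difficulty is then who contributes. A patient needs tumour at surgery to have a change value, and having tumour at surgery is close to the complement of the primary outcome. If cetuximab raises pCR as hypothesised, the two arms lose different proportions of patients. The comparison no longer rests on the randomised groups, and a cetuximab effect on a marker could appear where there is none.

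**Working it through.** **The plan's own figure.** Exact-binomial power of the uncorrected Pearson chi-square test, 54 per arm, 18% versus 43%, two-sided 0.05, is 81.9%, as stated in 12.1. The documents give no power, SD, correlation or effect size for the biomarker comparison. Those values below are assumptions, shown as ranges.

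**Patients with surgical tumour.** Taking non-pCR as a proxy for tumour present:
- Ixabepilone: 54 × (1 − 0.18) = 44.3, about 44.
- Combination: 54 × (1 − 0.43) = 30.8, about 31.
- Together: 75 of 108, or 69%.

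**Within-arm contrast.** Let n be the number of pairs, ρ the baseline–surgery correlation, SD 1 at each time, and Δ = 0.4 the shift.
- The unpaired test uses standard error √(2/n). The true one is s = √(2(1−ρ)/n).
- True size ≈ 2[1 − Φ(1.96/√(1−ρ))].
- Unpaired power ≈ Φ((Δ − c)/s) + Φ((−Δ − c)/s), with c = t(0.975, 2n−2) × √(2/n). For n = 44, c = 0.424.
- Paired power comes from the noncentral t with n−1 df and δ = Δ√n/√(2(1−ρ)).

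For n = 44:

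| ρ | True size, unpaired | s | Unpaired power | δ | Paired power |
|---|---|---|---|---|---|
| 0.3 | 1.9% | 0.178 | 45% | 2.24 | 59% |
| 0.5 | 0.6% | 0.151 | 44% | 2.65 | 74% |
| 0.7 | 0.04% | 0.117 | 42% | 3.43 | 92% |

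The unpaired formula treats the pooled SD as known. Simulation without that shortcut gives 45/44/43% unpaired and about 60/73/92% paired. With 31 pairs, simulated power is 31/29/24% unpaired versus 44/58/80% paired. At ρ = 0 the unpaired test has its nominal 5% size. At ρ = −0.3 its size would be 8.6%, so the word conservative depends on positive correlation.

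**Between-arm contrast, precision.** The difference in change detectable with 80% power is 2.80 × √(1/n₁ + 1/n₂). That is 0.54 SD with 54 and 54, and 0.66 SD with 44 and 31.

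**Selection.** Simulate per-patient change with mean 0 and SD 1 in both arms. Let pCR follow a logistic model in the change, with intercepts set to give 18% and 43%, and analyse non-pCR patients only. Rates are for a single marker at nominal 5%, before the Benjamini-Hochberg adjustment:

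| pCR log-odds per SD of change | Between-arm rejections (bias) | Within-arm paired test, 18% arm (bias) | Within-arm paired test, 43% arm (bias) |
|---|---|---|---|
| 0 | 5% (0) | 5% (0) | 5% (0) |
| 0.5 | 8% (0.12 SD) | 9% (0.09 SD) | 21% (0.21 SD) |
| 1 | 14% (0.20 SD) | 19% (0.16 SD) | 55% (0.36 SD) |
| 2 | 29% (0.28 SD) | 42% (0.24 SD) | 93% (0.52 SD) |

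A second model, in which change correlates 0.3/0.5/0.7 with an underlying pCR liability, gives 7.8/13.4/23.5% between arms, and about 5% when every patient is measured. Within an arm the selection bias is not offset by the other arm, so the paired test is the more exposed of the two.

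**The case against.** The strongest reply is that the sentence most naturally means a comparison of the two arms on the baseline-to-surgery difference, for which an unpaired t-test is correct. That stands. A reader might infer that the test misleads under either reading; the documents do not support this. Between arms the test is sound, and selection distorts it only if pCR differs by arm and depends on marker change. Such dependence is plausible: section 1.3 sets out to correlate these markers with response. The paired biopsies from the cetuximab–carboplatin trial summarised in 4.0.3 also point that way, but in only seven informative patients.

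A reader might also infer that surgical samples exist only in patients with residual tumour. That is a reasonable inference for most patients but is not stated. The T-A grade includes near-total effect, so some pCR patients may still have tumour. The schedule in section 2.0 also lists an optional "Serum sample for biomarkers expression at baseline, and at the time of surgery", which needs no tumour, although section 3.0.2 describes only a pre-treatment blood sample.

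Two further extensions go too far. One could imagine all 54 baselines being set against residual tumours only, which can create false changes, but nothing in the plan proposes it. Patients who change regimen raise a fair question, since section 3.0.3 says "Any patient, who switches to another neoadjuvant therapy prior to surgery, will be asked to undergo an additional breast biopsy". That biopsy is optional and needs separate consent, and the documents give no number of switchers, so no size can be attached.

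Finally, the analysis is exploratory. That also stands, and it sets the weight of the point.

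**Conclusion.** The point holds in limited form. Section 12.2 leaves the contrast undefined. If it is run within an arm, the named test is wrong: size falls to about 2% or less, and power for a 0.4 SD shift with 44 pairs is about 43–45% instead of about 60–92%, for assumed correlations of 0.3 to 0.7. The error there is lost power, not false positives, as long as the correlation is positive.

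If it is run between arms on change, the test is right but the population is selected after randomisation. False positives range from 5% with no dependence between change and pCR to about 29% under the strongest dependence examined. That range assumes the design pCR rates come true and that tissue is missing exactly in pCR patients.

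The primary pCR comparison and the secondary analyses do not use this test. This is a minor correction.

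**What to change.** In section 12.2:
- State which contrast or contrasts are intended.
- For any within-arm baseline-to-surgery comparison, use a paired t-test (signed-rank test for IHC scores) in patients with both samples.
- For the between-arm comparison, keep the two-sample t-test and say that it is applied to per-patient change.
- Keep the Benjamini-Hochberg adjustment.
- Report the number of patients with paired tissue by arm and by pCR status.
- Label both the within-arm and the between-arm results as conditional on tumour being present at surgery, and not as intention-to-treat comparisons.

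The cost is SAP wording and one extra table of counts; no sampling or sample size changes. The labels disclose the selection but do not remove it. The within-arm results need the label at least as much as the between-arm one, since the paired test cures the pairing error and not the selection.
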